1.3.3 Methods of Analysis

Rituximab + IVIG for Desensitization

We aim to recruit 75 HS patients on the basis of a clinically relevant increase in the absolute rate of transplantation for highly-HLA sensitized deceased donor recipients of approximately 50 percentage points between the two groups during 9 months of follow-up, with an estimated event rate of 15% in the control UNOS study group. We determined that this number of patients would provide the study with a power of 95%, with a two-sided type I error of 5% and a nonadherence or loss to follow up rate of 5(or 10)%. A transplant rate of 60-70% in the intervention limb is based on our experience with desensitization in the recent years (49, 113, 131). All analyses shall be performed on the basis of the intention-to-treat principle. Patients that were transplanted outside of the study will be included in the analysis.

We shall compare the proportions of patients in the treatment group compared to the UNOS control group using time-to-event analysis with respect to outcomes such as the primary outcome (rate of transplantation) and certain secondary outcomes (such as recipient and graft survival, occurrence of rejection in the treatment group only). These outcomes shall be analyzed with the use of the log-rank test. Cox proportional-hazards regression shall be used to obtain unadjusted hazard ratios and to adjust for significant stratifying variables and to test for effect modification in all secondary analyses. Data from patients who are lost to follow-up shall be regarded as censored at the time of the last contact. Data from patients who do not receive transplantation shall be censored at end of 9 months post desensitization. We shall use Kaplan–Meier estimates of the proportion of patients with the above listed outcomes. We shall calculate the number of patients who would need to be desensitized to allow one deceased donor renal transplant from the hazard ratio and its 95% confidence interval.

For other outcomes, the Chi square or Fischer exact test shall be used if the variable is categorical, and the t-test or signed rank test if it is continuous variable.

To determine whether the treatment effect varies according to the patients' PRA status, a priori subgroup analysis shall be planned with patients stratified according to the titer of PRA (>80% or <80%), and a test of interaction shall be performed in a Cox model. Post hoc subgroup analyses shall be conducted with the use of other stratifying variables. Treatment effects shall be described in terms of hazard ratios and absolute risk differences with 95% confidence intervals. All P values reported shall be two-sided and adjudged significant if <0.05.

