Rates of transplantation for highly-HLA sensitized patients (HS) are exceedingly low (<10% of patients with PRAs > 30% receive DD kidneys each year). IVIG 10% has been demonstrated as an effective desensitization agent in placebo controlled trials (1). However, in this study, only 35% of treated patients vs 17% placebo were able to receive a working kidney transplant, most from DD. Recent uncontrolled data from our group demonstrated a robust effect on improvement of transplant rates for HS patients (80% treated) using a combination of IVIG + rituximab (2,3). This was also associated with improved reductions in donor-specific antibody levels (DSA) and flow-cytometry crossmatches at the time of transplant (4-8). This protocol appeared to be particularly effective in improving rates of transplantation for HS patients awaiting DD transplantation. Our group has also developed novel methodologies to predict the risk of antibody-mediated rejection (ABMR) post-transplant based on DSA and FCMX results after desensitization. This allows us to improve the prediction of acceptable donor-specific antibody (DSA) levels that are permissive for allowing transplantation to go forward (3-8).

With these considerations and observations in mind, we have formulated the following hypothesis. We believe that the addition of the novel B-cell depleting agent (Rituximab) to IVIG treatment will offer significant benefits in reducing anti-HLA (DSA) thus improving rates and outcomes of DD transplantation above that seen for highly-HLA sensitized patients awaiting DD transplant on the UNOS list. In addition, we will assess the ability of Rituximab to lower DSA levels and reduce allograft injury post-transplantation. Protocol biopsies will be performed at time of transplant and at 12M post-transplant to determine the incidence of chronic antibody mediated rejection (Transplant Glomerulopathy {TG}). These biopsies will be read by the pathologist at participating institutions and graded according to Banff Criteria (2005) (9).

TARGET POPULATION:

Patients with end-stage renal disease on dialysis (ESRD, CKD Stage V), ages 18-65 years who are awaiting deceased donor (DD) kidney transplantation on the UNOS wait list have a Panel Reactive Antibody (PRA) >30% and a significant sensitization history (previous pregnancies, blood transfusions and/or previous transplants) with sufficient wait time to allow frequent DD offers with positive crossmatches (CMXs) that prohibit transplantation.

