1.0 STATISTICAL CONSIDERATIONS

1.1 IVIG + Rituximab for Desensitization

Primary Objective:

This trial is designed to determine if Rituximab + IVIG is effective in improving rates of transplantation for highly-HLA sensitized DD candidates on the UNOS waiting list over a 9M period of time after completion of treatment. Results will be compared to transplant rates in a group of age and anti-HLA antibody matched patients who remain on the UNOS wait list during the study period. This is the PRIMARY END POINT. Secondary end points include and will be evaluated based on time line in appendix A:

Transplantation rate assumptions:

- 60-65% in the IVIG + Rituximab group
- ~15% in the non-desensitized patients on UNOS wait list

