1.2 Target Sample Size

The target sample size is based on the statistical estimates of adequate sample size to power the study at 95% confidence. 95% Confidence Intervals for the 12-month Transplant Rate Assumes a 50% transplant rate (Expected proportion = 0.50) at 12 months for IVIG + Rituximab

Confidence interval for proportion using normal approximation (n large)

	1	2	3
Confidence level, 1-□	0.95	0.95	0.95
1 or 2 sided interval?	2	2	2
Expected proportion, □	0.50	0.50	0.50
Distance from proportion to limit, □	0.127	0.117	0.113
n	60	70	75

We do not have a good estimate of the IVIG + Rituximab transplant rate at 12 months in this patient population. We expect the rate to be at least 50%, hopefully as high as 60 to 65%. This is based on our experience over the past 7 years where 67% of deceased donor recipients were transplanted after desensitization (Vo et al. Transplantation 2013;65:1-7). This article is included. Thus these estimates are reliable in our hands.

For estimation using a 95% confidence interval, the assumed 50% transplant rate is conservative in that the width of the 95% confidence interval will be maximum when the assumed rate is 50%, i.e. the estimate will be least precise when the assumed rate is 50%.

Table 3 shows the upper limit of the 95% confidence interval estimates of the historical transplant rate at 3 years to be about 32% (highest at 38% in 2006).

Column 3 (Distance from proportion to limit) in the above power and sample size table shows that the lower limit of the 95% confidence interval for the IVIG + Rituximab transplant rate at 12 months (assuming the rate = 50%) is about 39% [50% – 11.3% = 38.7%], which is higher than the upper limit of the 95% confidence interval for the historical rate at 3 years (even in 2006).

If the observed IVIG + Rituximab transplant rate is > 50%, then the lower level of the 95% confidence interval will be > 39% and the evidence for the effectiveness of IVIG + Rituximab will be stronger.

For example, if the observed transplant rate is 60%, then the 95% confidence interval (based on n = 75) is approximately 49% to 71%.

[As I wrote in the document: “If the observed 12-month IVIG + Rituximab transplant rate is > 50%, then the effectiveness evidence is even stronger (the lower limit of the CI will be higher).”]

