1.3.1 Primary Efficacy Variables

The primary efficacy variable is the number of highly-HLA sensitized patients receiving a deceased donor transplant within 9 months after completion of the treatment. From our previous experience, the anticipated transplant rates for patients receiving IVIG + Rituximab desensitization is ~70% (49,112, 131). The rates for DD transplantation in non-treated patients based on sensitization levels is shown in Figure 15 below. Briefly, the rates of transplantation for all sensitized patients are <12% per year for the past decade. This indicates that desensitization

with IVIG + Rituximab is likely to benefit this high risk group who are otherwise unlikely to receive a life-saving transplant.

[figure not shown]

Figure 15: Data shown in figure 14 represent an analysis of 95,083 deceased donor transplants performed over the 10 year period 2000-2009. When analyzed by PRA status, one can see that <20% of all transplants performed are in highly-HLA sensitized patients. Data from the United States Renal Data Systems (usrds.gov) for 2009 also show that the wait time for a deceased donor kidney for patients with PRAs <10% is 4 years but increases to 8 years for patients with PRAs >10%. These trends have not changed over the past decade.

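### The 15% control transplant rate at 9 months is higher than every UNOS/USRDS background rate in the documents, which imply about 6-9% and at most 11.3%

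*Combined protocol and SAP*

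**What the plan says.** Section 1.1 lists two planning rates: "60-65% in the IVIG + Rituximab group" and about "15% in the non-desensitized patients on UNOS wait list". Neither line carries a time unit, but the objective above them refers to 9 months after completion of treatment.

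Section 1.3.3 puts the same control rate into the power statement: "with an estimated event rate of 15% in the control UNOS study group". The difference planned for there is "approximately 50 percentage points between the two groups during 9 months of follow-up", and the section claims 95% power at a two-sided 5% level with 5 (or 10)% loss.

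Elsewhere the documents describe how often untreated sensitized candidates are transplanted:

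- The protocol's opening background paragraph: "<10% of patients with PRAs > 30% receive DD kidneys each year".
- Section 1.3.1: "the rates of transplantation for all sensitized patients are <12% per year for the past decade".
- Section 1.2, describing the upper 95% confidence limit of "the historical transplant rate at 3 years to be about 32% (highest at 38% in 2006").
- Section 1.3.1, on USRDS waiting time, which "increases to 8 years for patients with PRAs >10" per cent.

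The text gives no derivation of the 15%. It states no hazard ratio, no number of controls and no expected number of control events.

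**The concern.** A cumulative probability at 9 months cannot exceed the one at 12 months. A 15% rate at 9 months therefore conflicts with background rates below 10% or below 12% per year, whatever the shape of the hazard.

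The 15% is an input to both the 50-point difference and the 95% power. It also bears on how much information the control group will supply. Sections 1.3.3 and the subgroup paragraph that follows plan a log-rank test, Cox hazard ratios with confidence intervals, a number needed to desensitize taken from the hazard ratio and its interval, and a test of interaction with PRA. With most treated patients expected to have the event, the precision of these estimates is limited mainly by the control events. A control rate set too high makes that precision look better than it will be.

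**Working it through.** **1. The plan's own figures.** The interval half-width in 1.2 reproduces: 1.96 × √(0.5 × 0.5 / 75) = 0.113. It does not use the 15%. The 95% power does not reproduce. For 15% versus 65%, two-sided 5%, the usual two-proportion formula needs 22 per group for 95% power, and 75 per group (equal groups assumed) gives more than 99.99%. If 75 is read as the total, 37 per group gives 99.8%.

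**2. Background rates on a 9-month scale.** Assuming constant hazard, p(9 months) = 1 − (1 − p)^(0.75/years).

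| Source | Stated | Calculation | 9 months |
|---|---|---|---|
| Opening background | <10% per year | 1 − 0.90^0.75 | <7.6% |
| 1.3.1 | <12% per year | 1 − 0.88^0.75 | <9.1% |
| 1.2, upper limit | 32% at 3 years | 1 − 0.68^0.25 | 9.2% |
| 1.2, upper limit for 2006 | 38% at 3 years | 1 − 0.62^0.25 | 11.3% |
| 1.3.1, as median | 8 years | 1 − 0.5^(0.75/8) | 6.3% |
| 1.3.1, as mean | 8 years | 1 − exp(−0.75/8) | 8.9% |

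The first four rows are upper bounds or upper confidence limits.

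**3. The 15% converted the other way.** Per year: 1 − 0.85^(4/3) = 19.5%. At 3 years: 1 − 0.85^4 = 47.8%, above both the 32% and the 38%.

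**4. Effect on the planned contrast.** The treated rate is held at 65%, the value that gives 50 points from 15%. The implied hazard ratio is ln(0.35)/ln(1 − c). Control events assume 75 controls, a number the plan does not give. The 95% interval factor is exp(1.96 × √(1/48.75 + 1/control events)), where 48.75 = 75 × 0.65 treated events.

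| Control rate c | Difference | Implied HR | Control events | HR interval | n per group, 95% power |
|---|---|---|---|---|---|
| 15% | 50.0 points | 6.5 | 11.25 | ×/÷ 1.9 | 22 |
| 11.3% | 53.7 points | 8.8 | 8.5 | ×/÷ 2.1 | 19 |
| 9% | 56.0 points | 11.1 | 6.75 | ×/÷ 2.2 | 17 |
| 6% | 59.0 points | 17.0 | 4.5 | ×/÷ 2.6 | 14 |

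**5. PRA interaction.** If patients and events split evenly between the two PRA strata (an assumption), the standard error of the log ratio of hazard ratios is twice that in step 4. The interval factor is ×/÷ 3.7 at 15% and ×/÷ 5.0 at 9%.

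**6. More controls.** With four controls per treated patient at 9%, control events are 300 × 0.09 = 27. The hazard-ratio factor is exp(1.96 × √(1/48.75 + 1/27)) = 1.6, and the interaction factor is about 2.6.

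**The case against.** **The 15% may be an annual rate.** Section 1.1 gives no time unit, and in 1.3.3 the 9 months is attached to the difference. Read as annual, 15% becomes 11.5% at 9 months and 38.6% at 3 years, close to the 2006 limit. This is a plausible explanation, but it does not remove the conflict. An annual 15% still exceeds the under-10% and under-12% figures and slightly exceeds 38% at 3 years, and 1.3.3 would still need correcting.

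**The source may lie outside the text available.** Section 1.2 refers to UNOS tables that are not in the text reviewed, and Figure 15 is not shown. A source for 15% could be there. This stands, so the fix allows for it.

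**The populations differ.** The quoted rates cover PRA >30%, all sensitized patients and PRA >10%, while the trial seeks candidates with enough wait time to receive frequent offers. That could raise their rate, but the plan matches controls only on age and antibody, and describes those offers as blocked by positive crossmatches. The one untreated figure near 15% is 17% in the placebo arm of an earlier IVIG trial. It is not a UNOS rate and has no stated period: over one year it would be 13.0% at 9 months, over two years 6.7%.

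**Single inputs are soft.** Constant hazard is assumed, and the 8-year wait is not labelled mean or median. The caption of Figure 15 describes transplants performed, so the under-12% figure may be a share of transplants and not a rate among candidates. Setting it aside leaves the other three sources, all below 15%.

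**No decision changes.** A lower control rate widens the difference and raises power, the worked basis for N=75 is the interval width, and the analysis uses observed controls. All of this is correct and limits the weight of the point.

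A reader might infer that the plan misstates its hazard ratio and expected control events. It states neither; those values, and the 75 controls behind them, are assumptions made here.

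**Conclusion.** The point holds as an unsupported planning rate. A 15% control rate over 9 months exceeds every UNOS/USRDS background figure in the documents. Those figures correspond to about 6-9%, or 11.3% on the most favourable one, under constant hazard; the conflict with the two annual rates needs no such assumption.

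The error is conservative for the overall test. A reader might infer that the trial is too small or its comparison biased, but the documents do not support that: fewer patients would be needed at the lower rates, and observed controls replace the planning rate in the analysis.

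What remains is that the 50-point difference and the 95% power rest on a rate the text does not justify. With 75 controls assumed, 4.5 to 8.5 control events would be expected instead of 11.25. The hazard ratio, the number needed to desensitize and the PRA interaction would then be less precise than the 15% suggests. With a larger registry group, that loss shrinks. The failure of the 95% power to reproduce is a separate fault, present at either control rate.

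**What to change.** - In 1.1 and 1.3.3, state the control rate as a 9-month probability with wait-listed candidates as the denominator (about 6-11% on the documents' figures). If 15% is kept, give its time unit and the source that supports it for the matched group.
- Recompute the difference and the stated 95% power from that rate, with the treated rate on the same 9-month basis.
- State the number of matched registry controls and draw several per treated patient. At 4:1 and a 9% rate, about 27 control events would narrow the hazard-ratio interval to about ×/÷ 1.6.

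The cost is SAP wording, one recalculation and extra registry data handling. Nothing changes for trial patients.

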This single (or multiple)-center, Phase I/II, exploratory study will use an open label design. The revision of this protocol is attributed to the failure of the placebo controlled protocol which showed a significant increase in SAEs in the IVIG + placebo group (3 antibody-mediated rejection episodes of 5 transplanted compared with 0 ABMR episodes in the IVIG + Rituximab group, $p=0.038$). The original study was put on hold and this iteration represents a redesign of the protocol to investigate the optimal dosing of Rituximab for desensitization and for modification of DSA levels post-transplant. The trial will examine the safety and efficacy of human polyclonal IgIV 10%, when given at [2.0 gm/kgx2], + Rituximab 1gm to reduce DSA to a level that is permissive for DD transplantation in 75 subjects (adults only ages ≥ 18 yrs) who are highly-HLA sensitized and are awaiting DD kidney transplant. Once transplant offers are entertained, a donor-specific crossmatch will be performed to detect anti-HLA antibodies which are associated with acute rejection or graft loss. (These anti-HLA antibodies may result naturally or from some previous pregnancy, transfusions, or prior transplants). If acceptable crossmatches and DSA levels are seen, the patients will proceed to DD transplantation. Patients receiving transplants will receive an additional dose of IVIG at transplantation (within 10 days) and will receive additional doses of Rituximab 1g) at 3M post-transplant if they remain or develop DSAs. OR at 6M if de novo DSAs occur (Fig 5 & 6). Patients who are desensitized and not transplanted within 9 M after desensitization will have completed the study and can be treated as best judged by the participating center. The protocol is shown in Figure 4 below.

[figure not shown]

Figure 4: Study Protocol for revised IVIG + Rituximab Study.

The decision to accept a DD transplant will rest entirely with the participating transplant center.

The subjects will be followed to determine the proportion who receive a transplant within 9M of completion of the infusions. In addition we will assess the transplanted patients to determine the number who sustain a viable and functioning kidney allograft for 12 months at which time a repeat study biopsy will be performed. All subjects will be evaluated on an intent-to-treat basis. The subject accrual rate will be limited to no more than five subjects per month in the initial three months to assure safety to all subjects.

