If the 9-month transplant rate is 50% (or 60 to 65%) then the 12-month rate should be even higher. During the placebo controlled phase of this study, the 13/15 patients were transplanted at a mean of 7 months post treatment. (7 IVIG + Placebo v. 6 IVIG + Rituximab). The mean wait time on dialysis for this group was > 11 years prior to being entered into the study and transplanted. Our original time of assessment of transplantation

was 6M. However, with this preliminary data, we felt it better to look at 9M since this would likely be more reasonable and would give a fair assessment of the efficacy of the therapy. We feel we are being conservative with these estimates. Hopefully, this clarifies the sample size calculation issues.

Column 1: the lower limit of the CI is 0.373 or about 37% when the sample size is 60.

Column 2: the lower limit of the CI is 0.383 or about 38% when the sample size is 70.

Column 3: the lower limit of the CI is 0.387 or about 39% when the sample size is 75.

If the upper limit of the UNOS CI (historical data) is below the lower limit of the above CI, then the CI do not overlap and there is evidence that IVIG + Rituximab is more effective re the 12-month transplant rate.

Given the UNOS data for transplant rates (Table 4 & 5), 60 should be sufficient as a sample size to show benefit of the IVIG + Rituximab treatment. However, 75 patients gives a better and more robust distinction. Since we will be looking at transplant rates at 9M post-treatment, and given the vagueness of organ allocation and patient readiness issues, we feel the choice of 75 patients will provide more security for an accurate and definitive study.

If the observed 12-month IVIG + Rituximab transplant rate is > 50%, then the effectiveness evidence is even stronger (the lower limit of the CI will be higher).

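### The non-randomised primary comparison has no pre-specified adjustment: the log-rank test and hazard ratio are unadjusted, and any Cox adjustment depends on significance and may cover secondary analyses only

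*Combined protocol and SAP*

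**What the plan says.** The Study Design section states that this "exploratory study will use an open label design". There is one treated group of 75 and no randomisation. The comparator is external. Section 1.1 says: "Results will be compared to transplant rates in a group of age and anti-HLA antibody matched patients who remain on the UNOS wait list". The matching ratio, the matching method and the number of controls are not given.

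Section 1.3.3 sets the analysis of the primary outcome (transplantation within 9 months) and of some secondary outcomes: "These outcomes shall be analyzed with the use of the log-rank test". It mentions no stratification, pairing or weighting. It continues: "Cox proportional-hazards regression shall be used to obtain unadjusted hazard ratios", and then "to adjust for significant stratifying variables"; the full clause reads "to adjust for significant stratifying variables and to test for effect modification in all secondary analyses". No covariates are listed. The only meaning given to significance is in the same section: "All P values reported shall be two-sided and adjudged significant if <0.05". The only stratifying variable named is PRA above or below 80%, and it serves a subgroup analysis and interaction test. Other stratifying variables are left to post hoc use.

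The number needed to desensitize for one transplant is to be computed from the hazard ratio and its confidence interval.

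The Target Population section and inclusion criterion 4 both require treated patients to have accrued enough wait time to receive deceased-donor offers.

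**The concern.** Without randomisation, the treated and control groups can differ in anything that affects the chance of an offer or of accepting one. Matching on age and antibody deals with two such factors. Wait time is another, and the protocol itself links it to offers by making it a condition of entry for treated patients. Nothing in the plan imposes the same condition on controls.

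The Cox sentence can be read in two ways, and neither secures adjustment of the primary comparison. If the closing reference to secondary analyses governs the adjustment, the primary comparison has none. If it governs only the test for effect modification, adjustment depends on a variable being significant, most naturally at p<0.05. A confounder matters through its imbalance and its effect on outcome, not through its p-value in one modest sample. At stake are the hazard ratio and the number needed to desensitize, which carries over any bias in that ratio.

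**Working it through.** **1. The planned effect as a hazard ratio.** Section 1.3.3 gives 15% in controls and a difference of about 50 points over 9 months, hence about 65% in treated patients. The plan states no hazard ratio. Under proportional hazards, HR = ln(1 − 0.65) / ln(1 − 0.15) = (−1.0498) / (−0.1625) = 6.46.

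The stated 95% power is not reproduced at these rates. Power is above 99.9% with 75 versus 75 and 99.8% with 75 in total. The gap is in the conservative direction, and this point does not depend on it.

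**2. Bias from one omitted factor (assumed inputs).** Suppose a binary factor multiplies the offer rate by r and is present in 80% of treated patients and 40% of controls, with no treatment effect. The spurious hazard ratio is approximately [1 + p1(r − 1)] / [1 + p0(r − 1)].
- r = 2: (1 + 0.8) / (1 + 0.4) = 1.8 / 1.4 = 1.29
- r = 3: (1 + 1.6) / (1 + 0.8) = 2.6 / 1.8 = 1.44

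Starting from a 15% control rate, 1 − 0.85^1.29 = 19% and 1 − 0.85^1.44 = 21%. That is a false difference of about 4 to 6 points.

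**3. Effect on the number needed to desensitize.** At face value, 15% versus 65% gives 1 / 0.50 = 2.0. Remove the bias from step 2:
- 6.46 / 1.286 = 5.02; 1 − 0.85^5.02 = 55.8%; 1 / 0.408 = 2.5
- 6.46 / 1.444 = 4.47; 1 − 0.85^4.47 = 51.7%; 1 / 0.367 = 2.7

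Now suppose a smaller observed effect, 30% versus 15% (assumed). HR = ln(0.70) / ln(0.85) = 2.19, and the apparent number is 1 / 0.15 = 6.7.
- 2.19 / 1.286 = 1.71; 1 − 0.85^1.71 = 24.2%; 1 / 0.092 = 10.8
- 2.19 / 1.444 = 1.52; 1 − 0.85^1.52 = 21.9%; 1 / 0.069 = 14.5

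**4. Error rate of the unadjusted test.** Simulation with no treatment effect, 75 versus 75 (control number assumed), 15% control rate, exponential times, censoring at 9 months, 2,000 replicates:

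| Prevalence, treated vs control | Factor HR | Unadjusted log-rank rejects |
|---|---|---|
| 50% vs 50% | 2 | 4.9% |
| 70% vs 40% | 2 | 7.3% |
| 80% vs 30% | 2 | 13.0% |
| 70% vs 40% | 3 | 12.0% |
| 80% vs 30% | 3 | 25.3% |

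A log-rank test stratified on the factor rejects in 4.4% to 5.6% of replicates in these settings.

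**5. What a p<0.05 screen would drop.** With 75 × (0.15 + 0.65) = 60 events and a factor of 50% prevalence, the chance of missing significance is 1 − Φ(√(60 × 0.25) × ln HR − 1.96). This gives 65% for HR 1.5, 23% for HR 2.0, 6% for HR 2.5 and 1% for HR 3.0.

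**The case against.** - **The controls are matched.** Section 1.1 matches on age and antibody, so a reader who takes the comparison to be unmatched goes too far. Individual matched sets should not be assumed either, because the wording fits group matching equally well. What stands is that the matching leaves out wait time and previous transplants, and that the planned test makes no use of it.
- **Selection by p-value is inferred.** No selection procedure is written, and the 0.05 threshold is stated for reported p-values. It is still the only meaning of significance that the plan offers. The other reading of the Cox sentence leaves the primary comparison with no adjustment.
- **The imbalance in wait time is not shown.** Section 1.2 says "The mean wait time on dialysis for this group was > 11 years", but that describes patients from the earlier placebo-controlled phase, not this trial's 75. No wait time is given for the controls, and 1.3.1 quotes 8 years for patients with PRA above 10%, so they may also have waited long. Treated patients are also selected for positive crossmatches, which could bias the other way. This limits any claim about size or direction. It does not supply the missing adjustment.
- **A strong confounder would usually pass a significance screen.** Step 5 bears this out. The risk from the screen lies mainly with moderate factors. The full bias in step 2 arises when the factor is not adjusted for at all, as in the log-rank test and the unadjusted hazard ratio.
- **The study is exploratory Phase I/II.** That is so, but the plan also claims 95% power at a two-sided 5% level, and 1.2 expects a definitive result. The non-overlap rule for confidence intervals in 1.2 is unadjusted too, so it offers no correction.

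**Conclusion.** The point holds as a recommended change. The plan tests a non-randomised comparison without adjustment, fixes no covariates, and leaves open whether the primary comparison is adjusted at all. It selects treated patients on wait time, which it links to offers and neither matches on nor commits to adjust for.

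On the assumed prevalences and effects, the hazard ratio is inflated by a factor of about 1.29 to 1.44. At the planned effect, the number needed to desensitize would read 2.0 instead of about 2.5 to 2.7. At an assumed 30% versus 15%, it would read 6.7 instead of about 10.8 to 14.5. The prevalences and factor effects have no source in the documents. The 60 events and the simulated error rates also assume 75 controls.

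Two stronger readings are not supported. One is that confounding could explain the planned result. A bias of 4 to 6 points cannot by itself produce a difference of 50. The other is that the confidence interval would be too narrow. Nothing in the documents establishes this, and ignoring the matching need not narrow an interval.

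**What to change.** In 1.3.3, make the main comparison of transplantation within 9 months a Cox model adjusted for a short list kept regardless of significance: accrued wait or dialysis time, PRA as a continuous variable, age, and number of previous transplants, as far as the control data hold them. Delete the word that ties adjustment to significance, and state that the adjusted model applies to the primary comparison. Derive the number needed to desensitize from the adjusted hazard ratio. Keep the unadjusted log-rank test as supportive.

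In 1.1, state the matching method and ratio. If controls are individually matched, account for it with strata or robust standard errors. If they are group-matched, the covariates suffice.

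The cost is SAP wording and a few degrees of freedom. With about 60 events, four covariates plus treatment leave 60 / 5 = 12 events per parameter. The listed baseline fields must be requested in the UNOS control extract. The documents do not show which are available, so this should be confirmed before the list is fixed.
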